5.1.2.4 Management of Increases in QT Interval

Study drug should be discontinued in patients who develop any of the following, unless there is a clear alternative cause for the changes:

- Sustained (at least two ECG measurements > 30 minutes apart) QTcF that is > 500 ms and > 60 ms longer than the baseline value
- Sustained absolute QTcF that is > 515 ms
- An episode of torsades de pointes or a new ECG finding of clinical concern

Of note, if there is a new intraventricular conduction block, the increase in QRS complex duration should be subtracted from the QTcF change, because this represents an increase in QTcF unrelated to alterations in repolarization. Therefore, it is critical that expert cardiology advice be sought to confirm any ECG changes and to ascertain the likelihood of a drug-induced arrhythmia versus the background occurrence of this arrhythmia. In such a situation, saving all available ECG data is highly suggested.

Management of patients with sustained QTcF prolongation should include close monitoring, with ECGs repeated at least hourly until two successive ECGs show resolution of the findings, correction of any electrolyte abnormalities, and possible discontinuation of other concomitant medications that are known to prolong the QT

interval. Consultation with a cardiologist or electrophysiologist is recommended, to help in the management of such patients.

5.2 SAFETY PARAMETERS AND DEFINITIONS

Safety assessments will consist of monitoring and recording adverse events, including serious adverse events and adverse events of special interest, performing protocol-specified safety laboratory assessments, measuring protocol-specified vital signs, and conducting other protocol-specified tests that are deemed critical to the safety evaluation of the study.

Certain types of events require immediate reporting to the Sponsor, as outlined in Section 5.4.

5.2.1 Adverse Events

According to the ICH guideline for Good Clinical Practice, an adverse event is any untoward medical occurrence in a clinical investigation subject administered a pharmaceutical product, regardless of causal attribution. An adverse event can therefore be any of the following:

- Any unfavorable and unintended sign (including an abnormal laboratory finding), symptom, or disease temporally associated with the use of a medicinal product, whether or not considered related to the medicinal product
- Any new disease or exacerbation of an existing disease (a worsening in the character, frequency, or severity of a known condition) (see Sections 5.3.5.8 and 5.3.5.9 for more information)
- Recurrence of an intermittent medical condition (e.g., headache) not present at baseline
- Any deterioration in a laboratory value or other clinical test (e.g., ECG, X-ray) that is associated with symptoms or leads to a change in study treatment or concomitant treatment or discontinuation from study drug
- Adverse events that are related to a protocol-mandated intervention, including those that occur prior to assignment of study treatment (e.g., screening invasive procedures such as biopsies)

5.2.2 Serious Adverse Events (Immediately Reportable to the Sponsor)

A serious adverse event is any adverse event that meets any of the following criteria:

- Is fatal (i.e., the adverse event actually causes or leads to death)
- Is life threatening (i.e., the adverse event, in the view of the investigator, places the patient at immediate risk of death)

This does not include any adverse event that, had it occurred in a more severe form or was allowed to continue, might have caused death.

- Requires or prolongs inpatient hospitalization (see Section 5.3.5.10)

GDC-9545—Genentech, Inc.
52/Protocol GO40987, Version 4

- Results in persistent or significant disability/incapacity (i.e., the adverse event results in substantial disruption of the patient's ability to conduct normal life functions)
- Is a congenital anomaly/birth defect in a neonate/infant born to a mother exposed to study drug
- Is a significant medical event in the investigator's judgment (e.g., may jeopardize the patient or may require medical/surgical intervention to prevent one of the outcomes listed above)

The terms "severe" and "serious" are not synonymous. Severity refers to the intensity of an adverse event (e.g., rated as mild, moderate, or severe, or according to NCI CTCAE; see Section 5.3.3); the event itself may be of relatively minor medical significance (such as severe headache without any further findings).

Severity and seriousness need to be independently assessed for each adverse event recorded on the eCRF.

Serious adverse events are required to be reported by the investigator to the Sponsor immediately (i.e., no more than 24 hours after learning of the event; see Section 5.4.2 for reporting instructions).

5.2.3 Adverse Events of Special Interest (Immediately Reportable to the Sponsor)

Adverse events of special interest are required to be reported by the investigator to the Sponsor immediately (i.e., no more than 24 hours after learning of the event; see Section 5.4.2 for reporting instructions). Adverse events of special interest for this study are as follows:

- Grade ≥ 3 nausea/vomiting/diarrhea
- Grade ≥ 2 thromboembolic events (pulmonary embolism, deep vein thrombosis, and embolism)
- Grade ≥ 3 Renal failure (including acute kidney injury or other similar medical concepts)
- Grade ≥ 3 hepatitis or elevation in ALT or AST
- Grade ≥ 2 vaginal or uterine hemorrhage
- Grade ≥ 2 bradycardia
- Any Grade of endometrial cancer
- Cases of potential drug-induced liver injury that include an elevated ALT or AST in combination with either an elevated bilirubin or clinical jaundice, as defined by Hy's Law (see Section 5.3.5.6)

- Suspected transmission of an infectious agent by the study drug, as defined below:
Any organism, virus, or infectious particle (e.g., prion protein transmitting transmissible spongiform encephalopathy), pathogenic or non-pathogenic, is considered an infectious agent. A transmission of an infectious agent may be suspected from clinical symptoms or laboratory findings that indicate an infection in a patient exposed to a medicinal product. This term applies only when a contamination of the study drug is suspected.

5.3 METHODS AND TIMING FOR CAPTURING AND ASSESSING SAFETY PARAMETERS

The investigator is responsible for ensuring that all adverse events (see Section 5.1.2 for definition) are recorded on the Adverse Event eCRF and reported to the Sponsor in accordance with instructions provided in this section and in Sections 5.4–5.6.

For each adverse event recorded on the Adverse Event eCRF, the investigator will make an assessment of seriousness (see Section 5.2.2 for seriousness criteria), severity (see Section 5.3.3), and causality (see Section 5.3.4).

5.3.1 Adverse Event Reporting Period

Investigators will seek information on adverse events at each patient contact. All adverse events, whether reported by the patient or noted by study personnel, will be recorded in the patient's medical record and on the Adverse Event eCRF.

After informed consent has been obtained but prior to initiation of study drug, only serious adverse events caused by a protocol-mandated intervention (e.g., invasive procedures such as biopsies, discontinuation of medications) should be reported (see Section 5.4.2 for instructions for reporting serious adverse events).

After initiation of study drug, all adverse events will be reported until 28 days after the final dose of study drug.

Instructions for reporting adverse events that occur after the adverse event reporting period are provided in Section 5.6.

5.3.2 Eliciting Adverse Event Information

A consistent methodology of non-directive questioning should be adopted for eliciting adverse event information at all patient evaluation timepoints. Examples of non-directive questions include the following:

"How have you felt since your last clinic visit?"

"Have you had any new or changed health problems since you were last here?"

5.3.3 Assessment of Severity of Adverse Events

The adverse event severity grading scale for the NCI CTCAE (v 5.0) will be used for assessing adverse event severity. [Table 2](#) will be used for assessing severity for adverse events that are not specifically listed in the NCI CTCAE.

Table 2 Adverse Event Severity Grading Scale for Events Not Specifically Listed in NCI CTCAE

Grade	Severity
1	Mild; asymptomatic or mild symptoms; clinical or diagnostic observations only; or intervention not indicated
2	Moderate; minimal, local, or non-invasive intervention indicated; or limiting age-appropriate instrumental activities of daily living ^a
3	Severe or medically significant, but not immediately life threatening; hospitalization or prolongation of hospitalization indicated; disabling; or limiting self-care activities of daily living ^{b, c}
4	Life-threatening consequences or urgent intervention indicated ^d
5	Death related to adverse event ^d

NCI CTCAE = National Cancer Institute Common Terminology Criteria for Adverse Events.

Note: Based on the most recent version of NCI CTCAE (v 5.0), which can be found at: http://ctep.cancer.gov/protocolDevelopment/electronic_applications/ctc.htm

- ^a Instrumental activities of daily living refer to preparing meals, shopping for groceries or clothes, using the telephone, managing money, etc.
- ^b Examples of self-care activities of daily living include bathing, dressing and undressing, feeding oneself, using the toilet, and taking medications, as performed by patients who are not bedridden.
- ^c If an event is assessed as a "significant medical event," it must be reported as a serious adverse event (see Section 5.4.2 for reporting instructions), per the definition of serious adverse event in Section 5.2.2.
- ^d Grade 4 and 5 events must be reported as serious adverse events (see Section 5.4.2 for reporting instructions), per the definition of serious adverse event in Section 5.2.2.

5.3.4 Assessment of Causality of Adverse Events

Investigators should use their knowledge of the patient, the circumstances surrounding the event, and an evaluation of any potential alternative causes to determine whether an adverse event is considered to be related to the study drug, indicating "yes" or "no" accordingly. The following guidance should be taken into consideration (see also [Table 3](#)):

- Temporal relationship of event onset to the initiation of study drug
- Course of the event, with special consideration of the effects of dose reduction, discontinuation of study drug, or reintroduction of study drug (as applicable)
- Known association of the event with the study drug or with similar treatments
- Known association of the event with the disease under study

- Presence of risk factors in the patient or use of concomitant medications known to increase the occurrence of the event
- Presence of non-treatment-related factors that are known to be associated with the occurrence of the event

Table 3 Causal Attribution Guidance

Is the adverse event suspected to be caused by the study drug on the basis of facts, evidence, science-based rationales, and clinical judgment?	
YES	There is a plausible temporal relationship between the onset of the adverse event and administration of the study drug, and the adverse event cannot be readily explained by the patient's clinical state, intercurrent illness, or concomitant therapies; and/or the adverse event follows a known pattern of response to the study drug; and/or the adverse event abates or resolves upon discontinuation of the study drug or dose reduction and, if applicable, reappears upon re-challenge.
NO	An adverse event will be considered related, unless it fulfills the criteria specified below. Evidence exists that the adverse event has an etiology other than the study drug (e.g., preexisting medical condition, underlying disease, intercurrent illness, or concomitant medication); and/or the adverse event has no plausible temporal relationship to administration of the study drug (e.g., cancer diagnosed 2 days after first dose of study drug).

For patients receiving combination therapy, causality will be assessed individually for each protocol-mandated therapy.

5.3.5 Procedures for Recording Adverse Events

Investigators should use correct medical terminology/concepts when recording adverse events on the Adverse Event eCRF. Avoid colloquialisms and abbreviations.

Only one adverse event term should be recorded in the event field on the Adverse Event eCRF.

5.3.5.1 Diagnosis versus Signs and Symptoms

A diagnosis (if known) should be recorded on the Adverse Event eCRF rather than individual signs and symptoms (e.g., record only liver failure or hepatitis rather than jaundice, asterixis, and elevated transaminases). However, if a constellation of signs and/or symptoms cannot be medically characterized as a single diagnosis or syndrome at the time of reporting, each individual event should be recorded on the Adverse Event eCRF. If a diagnosis is subsequently established, all previously reported adverse events based on signs and symptoms should be nullified and replaced by one adverse event report based on the single diagnosis, with a starting date that corresponds to the starting date of the first symptom of the eventual diagnosis.

5.3.5.2 Adverse Events That Are Secondary to Other Events

In general, adverse events that are secondary to other events (e.g., cascade events or clinical sequelae) should be identified by their primary cause, with the exception of severe or serious secondary events. A medically significant secondary adverse event that is separated in time from the initiating event should be recorded as an independent event on the Adverse Event eCRF. For example:

- If vomiting results in mild dehydration with no additional treatment in a healthy adult, only vomiting should be reported on the eCRF.
- If vomiting results in severe dehydration, both events should be reported separately on the eCRF.
- If a severe GI hemorrhage leads to renal failure, both events should be reported separately on the eCRF.
- If dizziness leads to a fall and consequent fracture, all three events should be reported separately on the eCRF.
- If neutropenia is accompanied by an infection, both events should be reported separately on the eCRF.

All adverse events should be recorded separately on the Adverse Event eCRF if it is unclear as to whether the events are associated.

5.3.5.3 Persistent or Recurrent Adverse Events

A persistent adverse event is one that extends continuously, without resolution, between patient evaluation timepoints. Such events should only be recorded once on the Adverse Event eCRF. The initial severity (intensity or grade) of the event will be recorded at the time the event is first reported. If a persistent adverse event becomes more severe, the most extreme severity should also be recorded on the Adverse Event eCRF. Details regarding any increases or decreases in severity will be captured on the Adverse Event Intensity or Grade Changes eCRF. If the event becomes serious, it should be reported to the Sponsor immediately (i.e., no more than 24 hours after learning that the event became serious; see Section 5.4.2 for reporting instructions). The Adverse Event eCRF should be updated by changing the event from "non-serious" to "serious," providing the date that the event became serious, and completing all data fields related to serious adverse events.

A recurrent adverse event is one that resolves between patient evaluation timepoints and subsequently recurs. Each recurrence of an adverse event should be recorded as a separate event on the Adverse Event eCRF.

5.3.5.4 Abnormal Laboratory Values

Not every laboratory abnormality qualifies as an adverse event. A laboratory test result must be reported as an adverse event if it meets any of the following criteria:

- Is accompanied by clinical symptoms
- Results in a change in study treatment (e.g., dosage modification, treatment interruption, or treatment discontinuation)
- Results in a medical intervention (e.g., potassium supplementation for hypokalemia) or a change in concomitant therapy
- Is clinically significant in the investigator's judgment

Note: For oncology trials, certain abnormal values may not qualify as adverse events.

It is the investigator's responsibility to review all laboratory findings. Medical and scientific judgment should be exercised in deciding whether an isolated laboratory abnormality should be classified as an adverse event.

If a clinically significant laboratory abnormality is a sign of a disease or syndrome (e.g., alkaline phosphatase and bilirubin $5 \times$ ULN associated with cholestasis), only the diagnosis (i.e., cholestasis) should be recorded on the Adverse Event eCRF.

If a clinically significant laboratory abnormality is not a sign of a disease or syndrome, the abnormality itself should be recorded on the Adverse Event eCRF, along with a descriptor indicating whether the test result is above or below the normal range (e.g., "elevated potassium," as opposed to "abnormal potassium"). If the laboratory abnormality can be characterized by a precise clinical term per standard definitions, the clinical term should be recorded as the adverse event. For example, an elevated serum potassium level of 7.0 mEq/L should be recorded as "hyperkalemia."

Observations of the same clinically significant laboratory abnormality from visit to visit should only be recorded once on the Adverse Event eCRF (see Section 5.3.5.3 for details on recording persistent adverse events).

5.3.5.5 Abnormal Vital Sign Values

Not every vital sign abnormality qualifies as an adverse event. A vital sign result must be reported as an adverse event if it meets any of the following criteria:

- Is accompanied by clinical symptoms
- Results in a change in study treatment (e.g., dosage modification, treatment interruption, or treatment discontinuation)
- Results in a medical intervention or a change in concomitant therapy
- Is clinically significant in the investigator's judgment

It is the investigator's responsibility to review all vital sign findings. Medical and scientific judgment should be exercised in deciding whether an isolated vital sign abnormality should be classified as an adverse event.

If a clinically significant vital sign abnormality is a sign of a disease or syndrome (e.g., high blood pressure), only the diagnosis (i.e., hypertension) should be recorded on the Adverse Event eCRF.

Observations of the same clinically significant vital sign abnormality from visit to visit should only be recorded once on the Adverse Event eCRF (see Section 5.3.5.3 for details on recording persistent adverse events).

5.3.5.6 Abnormal Liver Function Tests

The finding of an elevated ALT or AST ($>3 \times$ baseline value) in combination with either an elevated total bilirubin ($>2 \times$ ULN) or clinical jaundice in the absence of cholestasis or other causes of hyperbilirubinemia is considered to be an indicator of severe liver injury (as defined by Hy's Law). Therefore, investigators must report as an adverse event the occurrence of either of the following:

- Treatment-emergent ALT or AST $>3 \times$ baseline value in combination with total bilirubin $>2 \times$ ULN (of which $\geq 35\%$ is direct bilirubin)
- Treatment-emergent ALT or AST $>3 \times$ baseline value in combination with clinical jaundice

The most appropriate diagnosis or (if a diagnosis cannot be established) the abnormal laboratory values should be recorded on the Adverse Event eCRF (see Section 5.3.5.1) and reported to the Sponsor immediately (i.e., no more than 24 hours after learning of the event), either as a serious adverse event or an adverse event of special interest (see Section 5.4.2).

5.3.5.7 Deaths

All deaths that occur during the protocol-specified adverse event reporting period (see Section 5.3.1), regardless of relationship to study drug, must be recorded on the Adverse Event eCRF and immediately reported to the Sponsor (see Section 5.4.2). This includes death attributed to progression of breast cancer

Death should be considered an outcome and not a distinct event. The event or condition that caused or contributed to the fatal outcome should be recorded as the single medical concept on the Adverse Event eCRF. Generally, only one such event should be reported. If the cause of death is unknown and cannot be ascertained at the time of reporting, "**unexplained death**" should be recorded on the Adverse Event eCRF. If the cause of death later becomes available (e.g., after autopsy), "unexplained death" should be replaced by the established cause of death. The term "**sudden death**" should not be used unless combined with the presumed cause of death (e.g., "sudden cardiac death").

If the death is attributed to progression of breast cancer, "breast cancer progression" should be recorded on the Adverse Event eCRF.

Deaths that occur after the adverse event reporting period should be reported as described in Section 5.6.

5.3.5.8 Preexisting Medical Conditions

A preexisting medical condition is one that is present at the screening visit for this study. Such conditions should be recorded on the General Medical History and Baseline Conditions eCRF.

A preexisting medical condition should be recorded as an adverse event only if the frequency, severity, or character of the condition worsens during the study. When recording such events on the Adverse Event eCRF, it is important to convey the concept that the preexisting condition has changed by including applicable descriptors (e.g., "more frequent headaches").

5.3.5.9 Lack of Efficacy or Worsening of Breast Cancer

Events that are clearly consistent with the expected pattern of progression of the underlying disease should not be recorded as adverse events. These data will be captured as efficacy assessment data only. In most cases, the expected pattern of progression will be based on RECIST criteria. In rare cases, the determination of clinical progression will be based on symptomatic deterioration. However, every effort should be made to document progression through use of objective criteria. If there is any uncertainty as to whether an event is due to disease progression, it should be reported as an adverse event.

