5.3.5.10 Hospitalization or Prolonged Hospitalization

Any adverse event that results in hospitalization (i.e., inpatient admission to a hospital) or prolonged hospitalization should be documented and reported as a serious adverse event (per the definition of serious adverse event in Section 5.2.2), except as outlined below.

An event that leads to hospitalization under the following circumstances should not be reported as an adverse event or a serious adverse event:

- Planned hospitalization required by the protocol for breast cancer surgery
- Hospitalization for a preexisting condition, provided that all of the following criteria are met:

The hospitalization was planned prior to the study or was scheduled during the study when elective surgery became necessary because of the expected normal progression of the disease

The patient has not experienced an adverse event

An event that leads to hospitalization under the following circumstances is not considered to be a serious adverse event, but should be reported as an adverse event instead:

- Hospitalization that was necessary because of patient requirement for outpatient care outside of normal outpatient clinic operating hours

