Appendix 1 Schedule of Activities

	Screening	In-Clinic Treatment		Surgery ^a	Post-Surgery Visit ^k
Day (Window)	(Day -28 to Day -1)	1	8 (±2)	15 (±2)	43 (±1 week)
Informed consent (Section 4.5.1) ^b	x				
Medical history, demographic data and baseline conditions (Section 4.5.2)	x				
Physical examination (Section 4.5.3)	x				x ^c
Height	x				
Weight	x				
Vital signs (Section 4.5.4)	x	x	x	x	x
ECOG performance status (Section 4.5.5)	x	x		x	x
Hematology (Section 4.5.9)	x ^d	x ^d	x	x	
Chemistry (Section 4.5.9)	x ^d	x ^d	x	x	
Coagulation (PT, aPTT, and INR) (Section 4.5.9)	x ^d	x ^d	x	x	x
FSH (Section 4.5.9) ^e	x				
Estradiol (Section 4.5.9) ^e	x				
Triplicate 12-lead ECG (Section 4.5.10)	x	x	x ^f	x ^f	
Tumor evaluation (Section 4.5.6)	x				
Tumor tissue (Section 4.5.9)	x			x or biopsy on Day 14	
Confirmation of available tissue sample	x				
Urinalysis (Section 4.5.9)	x				

GDC-9545—Genentech, Inc.
80/Protocol GO40987, Version 4

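### Section 5.3.5.9 sends clear, non-fatal breast cancer progression to RECIST-based efficacy data for which the protocol defines no assessment, endpoint or analysis

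*Combined protocol and SAP*

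**What the plan says.** Section 5.3.5.9 opens with an exclusion: "Events that are clearly consistent with the expected pattern of progression of the underlying disease should not be recorded as adverse events". It then names the destination and the usual yardstick: "These data will be captured as efficacy assessment data only. In most cases, the expected pattern of progression will be based on RECIST criteria". Symptomatic deterioration is allowed as a rarer basis. The section closes by sending any event of uncertain cause to the adverse event form.

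Other sections bear on the same events:

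- Section 5.2.1 counts as an adverse event "Any new disease or exacerbation of an existing disease" and refers the reader to Sections 5.3.5.8 and 5.3.5.9.
- Section 5.3.5.7 requires all deaths in the reporting period on the Adverse Event eCRF. "This includes death attributed to progression of breast cancer", and the term to enter is breast cancer progression.
- Section 5.3.5.10 exempts some admissions for a preexisting condition from reporting. One qualifying case is an admission "scheduled during the study when elective surgery became necessary because of the expected normal progression of the disease", provided the patient has also had no adverse event.
- Appendix 1 has a row "Tumor evaluation (Section 4.5.6)", marked in the screening column only.

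**The concern.** An exclusion from adverse event reporting is reasonable when the excluded events are captured elsewhere under a defined criterion. That suits a trial with a response or progression endpoint. This is a two-week preoperative study whose activity endpoint is a tissue proliferation marker, so the exclusion operates but its destination does not exist.

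The patients are untreated and operable, and they receive an investigational drug before definitive surgery. Section 1.3 supports the benefit-risk case partly by saying there is no evidence that the drug affects operability. Worsening seen during the window is the kind of observation that bears on that statement, and the safety report should be able to show it.

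**Working it through.** The plan gives no figure on this point and no arithmetic applies. The check sets the sections side by side.

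**Step 1. Does the destination exist?** A RECIST-based data stream needs a criterion, an assessment, an endpoint and an analysis.

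| Element | What the protocol provides |
|---|---|
| Criterion | RECIST is named once, in Section 5.3.5.9. Nothing says who applies it or to what imaging. |
| Assessment | Section 4.5.6 requires a baseline ultrasound. Appendix 1 marks tumor evaluation at screening and in none of the four later columns (Day 1, Day 8, surgery, post-surgery visit). |
| Endpoint | Sections 2.1 to 2.4 list safety, steady-state concentration, Ki67 change and exploratory biomarkers. Section 3.3.2 places traditional efficacy endpoints in Study GO39932. |
| Analysis | Section 6.6 analyses Ki67. Section 6 has nothing on tumor size, response or progression. |

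The tally is no mention of RECIST outside Section 5.3.5.9, no response or progression endpoint, and no scheduled post-baseline tumor evaluation.

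**Step 2. What do the recording rules do together?** Section 5.2.1 treats worsening of an existing disease as an adverse event. Section 5.3.5.8 says a condition present at screening is recorded if it worsens. Section 4.5.3 says new or worsened clinically significant examination findings are adverse events. Section 5.3.5.9 says the opposite for clear progression of the cancer. Section 5.3.5.7 restores recording, but only for deaths. The summaries in Section 6.4 are built from recorded adverse events, so clear, non-fatal progression handled under Section 5.3.5.9 does not reach them.

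**Step 3. What traces remain?**

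| Trace | Source | Why it does not identify progression |
|---|---|---|
| Uncertain events reported as adverse events | 5.3.5.9 | Catches the ambiguous cases; the clear ones are those excluded |
| Worsened post-surgery examination findings | 4.5.3 | Limited, symptom-directed examination; conflicts with 5.3.5.9 |
| Sonographic measurements before surgery | 4.5.6 | Entered in the eCRF, but no scheduled visit, progression threshold or planned analysis |
| Planned versus actual surgery | 4.5.8 | Both recorded; no reason for a change is requested |
| Reasons for stopping treatment or leaving the study | 4.6.1, 4.6.2 | Summarized under 6.2 and 6.4, but progression is in neither list of reasons |

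**Step 4. Hospitalization.** The exemption in Section 5.3.5.10 needs two things together: an admission planned before the study, or scheduled for elective surgery that expected progression made necessary; and no adverse event. Because Section 5.3.5.9 says clear progression is not an adverse event, such progression does not by itself defeat the second condition.

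**The case against.** The strongest reply is that this is leftover wording with little practical effect. With no RECIST assessment and about 14 days of treatment, a site would seldom be certain that an event is progression, and the closing sentence of Section 5.3.5.9 then sends it to the adverse event form. Much of this stands, and it rules out several stronger readings.

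- A reader might infer that worsening goes unrecorded unless it is fatal. The documents do not support that. Five indirect traces exist, and discontinuation reasons are summarized, so loss of operability that led to withdrawal could appear there.
- A reader might infer that Section 5.3.5.10 exempts any admission caused by progression. It does not. An unplanned admission for worsening cancer does not meet its conditions.
- A reader might take Section 1.3 to assert that the drug has no effect on operability. It reports only an absence of evidence of one.
- A reader might attach a confidence bound to a zero count of progression. The plan contains no such output, and the denominators are not fixed: enrollment is approximate, discontinued patients are replaced, and every dosed patient counts for safety.

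It is also fair that recording alone adds no assessment. Worsening would still be seen only when someone notices it. All cohorts receive the drug, so a listing cannot show that the window caused harm. Nodal or distant disease first found at or after surgery may have been present but undetected at baseline.

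What the reply does not remove is the operative instruction. Where a site is clear that the cancer has worsened, the text tells it not to use the one form that would name the event, and the alternative it offers does not exist.

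**Conclusion.** The point holds in limited form. Section 5.3.5.9 excludes clear, non-fatal progression from the adverse event data and assigns it to RECIST-based efficacy data that the protocol does not define, schedule or analyse. The remaining traces are indirect and none identifies progression.

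The size is a gap in the safety record, not a bias in the Ki67 analysis. The documents give no progression rate. That events will be few is an assumption, based on the short treatment period. The conclusion also assumes that sites follow Section 5.3.5.9 as written and that no collection rule outside these documents fills the gap. The change should be made, because the text contradicts its own neighbouring sections and the correction is cheap.

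**What to change.** 1. In Section 5.3.5.9, delete the RECIST and efficacy-data sentences. Replace the exclusion with a rule that observed worsening of the breast cancer from Day 1 to the post-surgery visit is recorded on the Adverse Event eCRF as *breast cancer progression*, the term already in Section 5.3.5.7.
2. Have sites note separately any disease first found at surgical staging that may have been present at baseline, so that it is not counted as progression by default.
3. Add to Section 6.4 a listing of these events by dose level.
4. Reconcile Section 5.3.5.9 with Sections 4.5.3 and 5.2.1 (worsening as an adverse event), and with Section 4.5.6 and Appendix 1 (ultrasound before surgery mentioned in the text, tumor evaluation scheduled at screening only).
5. Keep the Section 5.3.5.10 exemption for planned admissions, and state that it does not cover hospitalization for recorded progression. Removing it altogether could make planned admissions for unrelated conditions reportable.

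The cost is protocol wording and one listing, with no new procedure. The downside is a few extra adverse event entries, some of them not drug-related.
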